All subjects, including those assigned to personalized care, will receive phone calls from clinical personnel within 1 month of enrollment. In order to minimize inconvenience, subjects will be asked their preferred times to be called at the time of enrollment. Staff contacting subjects in the personalized care group will have access to NMR values when they become available in the study's secure REDCap database. With the aid of a written script, staff will provide participants a personalized (based on NMR) verbal description of smoking cessation medications they are eligible to take (as determined by study physician), including efficacy and common side effects. If subjects would like to take a smoking cessation medication, they will be allowed to choose from those they are medically able to receive, and the study physician will call a prescription into an outpatient pharmacy (with which arrangements have been made to have medication costs billed to the study rather than the subject). Regardless of whether subjects choose to receive a prescription for a medication, they will be offered referral to their state Tobacco Quit Line for smoking cessation counselling via an online portal. This portal will track the patient's progress through the quit line process and these data may be collected for research purposes. Verbal instructions will be provided to participants given prescriptions to contact their primary provider and the research study staff (during regular business hours) in case of adverse effects of a medication. They will also be instructed to call 911 if they believe they are having a medical emergency.

Follow up phone calls

Study RAs will call subjects at approximately 1, 3 and 6 months post-intervention phone call to assess smoking behavior, self-reported adherence, and side effects including neuropsychiatric side effects. Study personnel will make up to 10 calls per follow up at different times of day and days of the week and call subjects' alternate contacts when needed. Participants will receive \$10 for each phone call that they complete.

Single arm crossover for subjects in Usual Care Group

Subjects in the Usual Care Group who are still smoking at 6 month follow up will receive an additional intervention from study staff. With the aid of a written script, staff will provide participants a

	Baseline	1 mo*	3 mo*	6 mo*	2 weeks*
Outcomes					
Demographics	Х				
Smoking behavior	Х	Х	Х	X	Х
Side effect screening	Х	Х	Х		

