Attitudes & Beliefs	Х			Х	
Patient satisfaction				Х	
Biochemical validation of cessation				X	
Biochemical validation of adherence (subset of participants)		X			
Medication use		Х	Х		Х

NMR) verbal description of smoking cessation medications they are eligible to take (as determined by study physician), including efficacy and common side effects. If subjects would like to take a smoking cessation medication, they will be allowed to choose from those they are medically able to receive, and a prescription will be called into an outpatient pharmacy by the study physician. The intent of this design is to assess the impact of a personalized message on medication uptake in

personalized (based on

Relative to 6-month follow-up (applies to subjects who are still smoking in Usual Care)

participants who failed to guit with the usual care treatment. The cost of medications will be the responsibility of participants who chose to have prescriptions filled. Participants provided prescriptions will be called by study staff in approximately 2 weeks to assess whether they have filled their prescriptions and are taking the medication.

EHR data collection

Prospective participants who are identified smokers in the VHVI clinic will have their EHR examined by study staff to determine eligibility, and EHR data collected in the screening form will be retained for future analysis. For enrolled participants, research staff will review the participant's EHR to collect relevant clinical data. Staff may review participant records for up to 5 years after enrollment.

Outcome assessment

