Subject outcomes will be assessed by phone approximately 1, 3 and 6 months post-intervention phone call. At follow up, a research assistant will complete interviews assessing smoking behavior, self-reported side effects, and measures of patient engagement and attitudes toward precision medicine. At approximately 1 month, a subset of participants will be selected to complete follow-up in person, where, in addition to an interview, they will have blood drawn to biochemically assess adherence by measurement of smoking cessation drug levels. Subjects will receive an additional \$10 for completing 1 month follow up in person. At approximately 6 months, subject outcomes may be assessed in person. Subjects self-reporting abstinence may have smoking status confirmed biochemically using end expired carbon monoxide. Biochemically validated abstinence will be defined as end expired carbon monoxide less than 10 ppm. Participants will receive \$10 for each of these completed calls and an additional \$10 if they participate in an end-expired carbon monoxide test at 6 months. This will be sent by mail in the form of a check. Participants in the single arm crossover group (i.e., those in the Usual Care group who were still smoking at 6 months) who accepted medication prescriptions will receive phone calls approximately 2 weeks after the second personalized intervention to assess whether they have filled the prescription. The most any one participant can be compensated (completing all surveys, the additional blood draw and biochemical validation) is \$60.00 over the course of approximately 6 months.

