Adverse drugs reactions: Subjects in this study will receive one of three FDA-approved smoking cessation therapies (NRT, varenicline, or bupropion) and will have the potential to experience drug-related side effects. Nicotine replacement therapy is generally very safe (it is sold over the counter). However, possible side effects include skin irritation or itching (patch), dizziness, headache, nausea, and rapid heartbeat. Common side effects of varenicline include nausea, sleep disturbance and vivid dreams, gastrointestinal symptoms, and vomiting. Very rarely, patients, particularly those with unstable psychiatric conditions, may experience symptoms such as behavioral changes, agitation, depressed mood, and suicidal behavior during varenicline treatment. Common side effects of bupropion include dry mouth, irritability, and difficulty sleeping. A large trial of over 8000 patients was presented at the Society for Research on Nicotine and Tobacco in Chicago in March, 2016, and did not demonstrate any difference in neuropsychiatric symptoms (including suicidal ideation and suicidal behavior) between patients on varenicline, bupropion, or nicotine replacement therapy (EAGLES; ClinicalTrials.gov Identifier: NCT01456936). Very rarely, patients can have seizures, especially in those with a history of seizures. To protect against risk from pharmacotherapy usage, this study will only use FDA-approved smoking cessation medications and tobacco treatment providers will screen patients to identify contraindications to NRT, bupropion or varenicline. Written and verbal instructions will be provided to patients given medication to contact their primary physician and the research PI, [name], in case of adverse effects of a medication. Additionally, RAs will call subjects at regular intervals (as described above) to monitor for serious side effects including neuropsychiatric side effects. Study personnel will make up to 10 calls per week at different times of day and days of the week and call subjects' alternate contacts when needed. Ultimately, the PI ([name]) will review any serious adverse events and report them appropriately to the IRB.

8.0 Reporting of Adverse Events or Unanticipated Problems Involving Risk to Participants or Others Any adverse events will be reported to the IRB according to IRB policies and procedures.

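### No scheduled side-effect check follows a study prescription issued at the 6-month crossover, although Section 7.0 relies on monitoring calls as one of its drug-safety protections

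*Protocol*

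**What the plan says.** In Section 6.0 of the protocol, the single-arm crossover offers usual-care subjects who are still smoking at 6 months an NMR-based message about the drugs open to them. If a subject wants one, "a prescription will be called into an outpatient pharmacy by the study physician". The subject pays for it.

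The follow-up of that prescription is described in three places:

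- Crossover paragraph: those given a prescription are "called by study staff in approximately 2 weeks to assess whether they have filled their prescriptions and are taking the medication".
- Outcome assessment paragraph: the call comes "approximately 2 weeks after the second personalized intervention to assess whether they have filled the prescription".
- Schedule table: the 2-week column is marked for smoking behavior and medication use. The row "Side effect screening" is marked at baseline, 1 month and 3 months only.

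Section 7.0 (adverse drug reactions) sets out how subjects are protected from drug risk. One element is that "RAs will call subjects at regular intervals (as described above) to monitor for serious side effects including neuropsychiatric side effects".

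**The concern.** Section 7.0 opens its drug-risk paragraph with subjects who receive one of the three drugs and makes no exception for those who start at the crossover. Someone assessing the risk section would reasonably conclude that staff call to ask about side effects during any course the study physician prescribes. For crossover prescriptions, Section 6.0 provides no such call.

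Two things are at stake. The protection described may differ from the protection delivered for this group. In addition, a side effect on a crossover drug would reach the study only if the subject volunteered it, even though staff are already due to telephone that subject about the same medication.

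**Working it through.** There is no sample-size or power figure to reproduce. The check is whether each call described in Section 6.0 covers side effects, and when it falls relative to the crossover.

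1. **Calls Section 7.0 can refer to.** It points back to calls already described. In Section 6.0, the calls with a side-effect component are those at about 1, 3 and 6 months after the intervention call, made to "assess smoking behavior, self-reported adherence, and side effects including neuropsychiatric side effects".
2. **Timing against the crossover.** The crossover is offered to subjects found to be smoking at the 6-month follow-up. The 1- and 3-month calls precede it and the 6-month call coincides with it. None falls during a drug course started at the crossover.
3. **Content of the one later call.** The crossover paragraph covers filling and taking the medication, the Outcome assessment paragraph covers filling only, and the table covers smoking behavior and medication use. The three differ slightly in scope, but none includes side effects.
4. **Count of scheduled side-effect assessments.**
   - After the first intervention call: 3 by the text (1, 3 and 6 months); 2 by the table (1 and 3 months).
   - After a crossover prescription: 0 by either text description; 0 by the table.
5. **Could another section close the gap?** Section 12.0 runs follow-up to about 6 months after the intervention call or, where applicable, after the start of pharmacotherapy. That wording might have been meant for later starters, but it defers to the study procedures, where the 2-week call is the last crossover contact. The EHR review of up to 5 years is for collecting clinical data and is not described as side-effect monitoring.

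The comparison also shows a second mismatch in the same table row. The follow-up call and Outcome assessment texts both have side effects assessed at 6 months, but the table leaves that cell blank. The finding about the 2-week call does not rest on this row alone, because both prose descriptions of that call agree with the table's blank.

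**The case against.** The strongest reply is that Section 7.0 limits itself by pointing back to the calls in Section 6.0, so it promises nothing beyond 1, 3 and 6 months. The crossover comes at the end of the study, the subject pays, and its declared purpose is to look at medication uptake. Lighter monitoring could be deliberate. This is a possible reading, and it is why one acceptable remedy is simply to state that scope. It does not remove the problem, because Section 7.0 does not say that crossover prescriptions fall outside the calls.

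Second, other protections remain, and this stands in full. Section 7.0 also provides for contraindication screening and for the principal investigator's review of serious adverse events. It further states: "Written and verbal instructions will be provided to patients given medication to contact their primary physician and the research PI". None of these is restricted to the first prescription, and the crossover script itself covers common side effects. A reader might infer that these subjects have no safety protection at all. The document does not support that. What is absent is the one element in which staff ask about side effects while the subject is on the drug; the rest act before prescribing or depend on the subject reporting.

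Third, a reader might infer that the Aim 1 side-effect rates will be biased, with crossover exposure appearing free of harm. That does not follow. Section 10.0 plans descriptive rates for each group and no crossover-specific rate. Counting events on an NMR-guided prescription as usual-care events would itself blur the comparison, and an unassessed period is not reported as zero events.

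**Conclusion.** The point holds in a limited form. After a crossover prescription the protocol schedules no side-effect assessment, and the monitoring calls named in Section 7.0 have no matching procedure for that group. This follows from the text alone and needs no numerical assumption. It concerns the period after the crossover only; the same subjects are asked about side effects earlier in follow-up.

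The number of people affected cannot be estimated usefully. Enrollment of 50 is a ceiling, and the protocol gives no allocation ratio, no expected 6-month abstinence in usual care and no expected uptake at the crossover. An accepted prescription is also not the same as a drug taken. A head count of exposed subjects would therefore rest on unsourced inputs. The group is a subset of one arm of a small pilot, so this is a modest but worthwhile correction to the protocol.

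**What to change.** Reconcile the crossover paragraph, the Outcome assessment paragraph and the schedule table in Section 6.0 with Section 7.0. There are two routes, and the choice belongs to the investigators:

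- Record side effects with the existing questions at the 2-week call already planned, mark the 2-week column accordingly, and report these events separately as post-crossover.
- Confine the Section 7.0 statement about monitoring calls to the first intervention, and disclose that crossover prescriptions are not actively screened for side effects.

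Under either route, give the 2-week call one consistent description in all three places, and reconcile the blank 6-month side-effect cell with the text that has side effects assessed at that call.

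The first route costs a few more minutes on an existing call, plus edits to text and table, with no new visit. The second costs wording only, but leaves side effects on crossover drugs to be learned from subjects' own reports.

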7.0 Risks

Risks of blood draw: Pain, redness, soreness, bruising, or infection may occur at the needle stick site. Rarely, some patients faint. We will protect against phlebotomy-related risk by collecting samples at the time of clinical sample collection when possible.

Expired Carbon Monoxide Test: There are no known serious adverse effects from this test. Sometimes people feel mildly short of breath or cough during the test.

Breach of Confidentiality: Medical information will be stored in a secure database. However, it is possible this database could be corrupted. Participant data will be collected using password-protected and encrypted computers, electronic medical records, and electronic participant tracking spreadsheets stored on a secure server. To prevent the loss of data, all electronic information is stored within the VUMC firewall and is password-protected. Only study staff will have access to the study data. Data quality (including visits completed during intervention window, data missingness, and recruitment rates) will be monitored monthly by the database manager and systematic data problems will be reported to the PI ([name]).

Adverse drugs reactions: Subjects in this study will receive one of three FDA-approved smoking cessation therapies (NRT, varenicline, or bupropion) and will have the potential to experience drug-related side effects. Nicotine replacement therapy is generally very safe (it is sold over the counter). However, possible side effects include skin irritation or itching (patch), dizziness, headache, nausea, and rapid heartbeat. Common side effects of varenicline include nausea, sleep disturbance and vivid dreams, gastrointestinal symptoms, and vomiting. Very rarely, patients, particularly those with unstable psychiatric conditions, may experience symptoms such as behavioral changes, agitation, depressed mood, and suicidal behavior during varenicline treatment. Common side effects of bupropion include dry mouth, irritability, and difficulty sleeping. A large trial of over 8000 patients was presented at the Society for Research on Nicotine and Tobacco in Chicago in March, 2016, and did not demonstrate any difference in neuropsychiatric symptoms (including suicidal ideation and suicidal behavior) between patients on varenicline, bupropion, or nicotine replacement therapy (EAGLES; ClinicalTrials.gov Identifier: NCT01456936). Very rarely, patients can have seizures, especially in those with a history of seizures. To protect against risk from pharmacotherapy usage, this study will only use FDA-approved smoking cessation medications and tobacco treatment providers will screen patients to identify contraindications to NRT, bupropion or varenicline. Written and verbal instructions will be provided to patients given medication to contact their primary physician and the research PI, [name], in case of adverse effects of a medication. Additionally, RAs will call subjects at regular intervals (as described above) to monitor for serious side effects including neuropsychiatric side effects. Study personnel will make up to 10 calls per week at different times of day and days of the week and call subjects' alternate contacts when needed. Ultimately, the PI ([name]) will review any serious adverse events and report them appropriately to the IRB.

8.0 Reporting of Adverse Events or Unanticipated Problems Involving Risk to Participants or Others Any adverse events will be reported to the IRB according to IRB policies and procedures.

9.0 Study Withdrawal/Discontinuation

Individuals who wish to withdraw from the study may do so at any time by contacting the Principal Investigator ([name]) in writing without penalization or change to their medical care. Any data collected prior to withdrawing from the study will be analyzed as enrolled unless requested for full withdrawal by the participant.

10.0 Statistical Considerations

This pilot project is intended to create infrastructure, establish feasibility, and provide necessary preliminary data to design and conduct a prospective RCT comparing tailored smoking cessation treatment to usual care. As such, we are not powered to detect differences between treatment groups in regards to primary or secondary outcomes. However, we will conduct descriptive and exploratory analyses of collected data as well as assess for between-group differences.

Aim 1. Develop infrastructure and procedures necessary to conduct a prospective randomized trial

comparing tailored smoking cessation treatment to usual care.

Hypothesis: We hypothesize that we will successfully: 1) enroll adult daily smokers from an outpatient clinic; 2) collect, process, store, and analyze relevant biologic samples; and 3) conduct follow-up assessments and accurately ascertain pertinent smoking cessation and patient care outcome measures.

Primary analysis: As a primary analysis, for each group we will calculate descriptive statistics for relevant demographic and clinical parameters, rates of enrollment and loss to follow-up, smoking cessation, and side effects. These data will be critical to inform future prospective studies.

Aim 2. Assess patient attitudes regarding personalized smoking therapy including: 1) interest in receiving personalized information, and 2) willingness to guide therapy based on personalized data. Hypothesis: A majority (>50%) of subjects will: 1) favorably view receiving personalized smoking information; and 2) express willingness to guide therapy based on personalized data.

Primary analysis: As a primary analysis, we will calculate the proportion of subjects that provided favorable responses (4 or 5 on Likert Scale) for questions addressing: 1) willingness to receive patient-specific smoking data; and 2) willingness to use these data to guide therapy, as reflected by the % who fill the prescription that is recommended by the NMR test results. We will also calculate rates of self-reported adherence, use of the quit line, and cessation at each follow up.

11.0 Privacy/Confidentiality Issues

Data will be placed into a password-protected, web-based database by study personnel. Only the research staff, the PI and co-investigators will have access to this data. A unique identification number will be used to protect the confidentiality of the study participants.

Protected Health Information (PHI) will be used in this study. The investigators will comply with the patient privacy guidelines of Vanderbilt University Medical Center and the rules outlined by the Health Insurance Portability and Accountability Act (HIPAA).

All research samples obtained for this study will be assigned a unique number. The key linking this unique number to PHI will be kept in a locked file. Only the investigator, co-investigators and research personnel will have access to the key and information that identifies participants as being in this study. Digital records will be stored on password-protected computers/servers. Digital data files will be coded so that the participant name or other such identifiers are not in the filename.

12.0 Follow-up and Record Retention

Subjects will be followed up through approximately 6 months after intervention phone call or postpharmacotherapy start date, if applicable (as outlined above in Study Procedure). Records will be kept indefinitely but will be destroyed if no longer needed.

